6.5.3 Rescue Medicine

Not Applicable

6.5.4 Non-Research Standard of Care

Not Applicable

7. STUDY INTERVENTION DISCONTINUATION AND

SUBJECT DISCONTINUATION/WITHDRAWAL

7.1 Halting Criteria and Discontinuation of Study Intervention

7.1.1 Individual Study Product Halting

Study product administration for any given subject may be stopped for SAEs, clinically significant adverse events, severe laboratory abnormalities, or any other medical conditions that indicate to the Investigator that continued dosing is not in the best interest of the patient.

For an individual subject, study product must be stopped if they have a suspected drug-related event of hypersensitivity (Grade 2 or higher) during or shortly after receiving the IP. While there are no criteria for grading “hypersensitivity” in the Division of AIDS (DAIDS) Table for Grading the Severity of Adverse Events, sites should use acute allergic reaction from that toxicity table. Subjects who have the study product stopped for a safety related issues will not continue with dosing. In addition, subjects who have an allergic reaction that is temporally associated with study product administration and the PI believes it to be related to study product will not receive any more study product.

In addition, a subject in this clinical study may discontinue study drug at their request for any reason. Every effort should be made to encourage subjects to remain in the study for the duration of their planned outcome assessments. Subjects should be educated on the continued scientific importance of their data, even if they discontinue study drug.

Unless the subject withdraws consent, those who discontinue study drug early will remain in the study. The reason for subject discontinuation of study drug should be documented in the case report form.

7.1.1.1 Remdesivir Halting

See Section 6.1.4. for information about dosing modifications due to laboratory abnormalities.

7.1.1.2 Oral Study Product Halting

See Section 6.1.4. for information about dosing modifications due to laboratory abnormalities.

The subject should not receive any additional oral study product if they develop any of the following conditions during the study:

- Active TB infection or evidence of latent TB (though testing is not required per protocol).
- VTE (DVT/PE).
- Suspected drug-induced liver injury with the appearance of fatigue, nausea, vomiting, right upper-quadrant pain or tenderness, fever, rash, and/or eosinophilia (>5%).
- New malignancy (except for successfully treated basal or squamous cell skin carcinoma)
- ALT or AST >8 times ULN

7.1.2 Study Halting

Given the potential severity of COVID-19, there are no pre-specified study stopping rules. Instead there will be close oversight by the protocol team and frequent DSMB reviews of the safety data.

7.2 Withdrawal from the Study

Subjects are free to withdraw from participation in the study at any time upon request, without any consequence. Subjects should be listed as having withdrawn consent only when they no longer wish to participate in the study and no longer authorize the Investigators to make efforts to continue to obtain their outcome data.

Subjects who withdraw from this study or are lost to follow-up after signing the informed consent form (ICF) and administration of the study product, will not be replaced. The reason for subject withdrawal from the study will be recorded on the appropriate CRF.

7.3 Lost to Follow-Up

A subject will be considered lost to follow-up if he or she fails to appear for all follow-up assessments. In lost to follow-up cases, attempts to contact the subject should be made and these efforts should be documented in the subject's records.

7.4 Readmission

If a subject is discharged from the hospital and then readmitted prior to Day 14, they may be given the remainder of the study product (i.e., infusion until Day 10 and oral product until Day 14). If the subject did not withdraw his/her consent to participate in the study, there is no need to re-consent upon readmission to the study hospital. However, the site will need to inform them that since he/she was readmitted, study product administration will resume and confirm that they still agree to receive study product. If the subject is re-admitted with diminished mental capacity, the site should discuss continued study participation with a LAR.

The study team will need to notify the study pharmacist of the readmission. The subject will not get the doses that they missed after being discharged. Upon readmission, the subject will get maintenance doses of infusion only since they already received the loading dose of the study product infusion on Day 1. No study product infusions should be given past Day 10 and no oral study product should be given past Day 14.

The site should not complete the Discontinuation of Treatment form in Advantage eClinical since the subject came back to the study hospital to be readmitted. For all data collection procedures required for those readmitted, please see the MOP.

8. STUDY ASSESSMENTS AND PROCEDURES

8.1 Screening and Efficacy Assessments

8.1.1 Screening Procedures

Screening procedures may be done over one to two calendar days (from Day -1 to Day 1). However, in many cases all the screening assessments can be done in less than 24 hours. If that is the case, Day 1 pre-study product administration baseline assessments, specimen collection and the initial study product administration can occur on the same calendar day as the screening procedures.

After the informed consent, the following assessments are performed to determine eligibility:

- Confirm the positive SARS-CoV-2 test result (per inclusion criteria).
- Take a focused medical history, including the following information:
 - Day of onset of COVID-19 signs and symptoms.
 - History of vaccinations within 4 weeks before screening and planned vaccinations.
 - Exclusionary vaccine history includes:
 - Has received any live vaccine (that is, live attenuated) within 4 weeks before screening, or intend to receive a live vaccine (or live attenuated) during the study. Note: Use of non-live (inactivated) vaccinations is allowed for all subjects.
 - History of chronic medical conditions, including chronic oxygen requirement, prior to onset of COVID-19. See conditions included in exclusion criteria (Section 5.2) and on the Medical History (CMX) data collection form.
 - History of medication allergies.
 - Medications and therapies for this current illness taken in the 7 days prior to Day 1, and history of any medication listed in the exclusion criteria.
 - Ask if they are participating in another clinical trial or plan to enroll in another clinical trial in the next 28 days.
- Women of childbearing potential should be counseled to either practice abstinence or use at least one primary form of contraception not including hormonal contraception from the time of screening through Day 29. Women should be confirmed to not be breastfeeding.
 - Note: If a woman is either postmenopausal (i.e., has had ≥ 12 months of spontaneous amenorrhea) or surgically sterile (i.e., has had a hysterectomy, bilateral ovariectomy (oophorectomy), or bilateral tubal ligation), she is not considered to be of childbearing potential.
- Height and weight (height can be self-reported).
- Results of recent radiographic imaging (x-ray or CT scan).
- SpO₂.

- Blood for screening laboratory evaluations if not done as part of routine clinical care in the preceding 48 hours:
 - CBC with differential
 - Evaluate if subject is neutropenic (absolute neutrophil count <1000 cells/ μL) ($<1.0 \times 10^3/\mu\text{L}$ or <1.0 GI/L) and/or lymphopenic (absolute lymphocyte count <200 cells/ μL) ($<0.20 \times 10^3/\mu\text{L}$ or <0.20 GI/L)
 - ALT and AST
 - Assess if ALT or AST > 5 times the upper limit of normal.
 - Creatinine (and calculate eGFR).
 - Determine if eGFR < 30 ml/min as these subjects are not eligible. Also, subject receiving hemodialysis or hemofiltration are not eligible.
 - Any automated calculation by the clinical laboratory or published formula for this calculation is acceptable. The site should select a formula to be used for all subjects enrolled at the site for the duration of the study.
- Urine or serum pregnancy test (in women of childbearing potential).

Clinical screening laboratory evaluations will be performed locally by the site laboratory. The volume of venous blood to be collected is presented in Table 3.

The overall eligibility of the subject to participate in the study will be assessed once all screening values are available. The screening process can be suspended prior to complete assessment at any time if exclusions are identified by the study team.

Study subjects who qualify will be randomized in the Advantage eClinical system, and all others will be registered as screen failures. The ordinal scale and the NEWS should be done at the time of randomization; the site will need this data to randomize the subject in eClinical. The study team has 24 hours to complete other Day 1 baseline assessments prior to the first study product administration including the collection of OP swab and blood and completing or recording a baseline physical examination that was done.

8.1.2 Efficacy Assessments

For all baseline assessments and follow-up visits, refer to the Schedule of Assessments (SOA) for procedure to be done, and details below for each assessment.

8.1.2.1 Measures of clinical support, limitations and infection control

The subject's clinical status will be captured on each study day while hospitalized through Day 29 or day after death whichever comes first. See more information about capturing death below. If a subject is discharged prior to Day 15, clinical status is collected on Day 15 and 29 if the subject returns for an in-person clinic visit or by phone if an in-person visit is not possible. Clinical status will also be captured on Day 22 during a phone visit. Clinical status is largely measured by the ordinal scale and the NEWS. Unlike the NEWS, the ordinal scale can also be evaluated over the

Appendix B - ACTT-2: Baricitinib/Remdesivir vs Remdesivir

phone if the discharged subject is unable to return for visits on Day 15 and 29 as well as on Day 22.

Except for on Day 1, when the ordinal scale and the NEWS is captured at the time of randomization, a site should try to complete the ordinal scale and the NEWS at approximately the same time each day. Ideally, complete the ordinal scale concurrently with NEWS just prior to study product administration, as time permits. The following measures are recorded for the ordinal scale:

- Hospitalization.
- Oxygen requirement.
- Non-invasive mechanical ventilation (via mask) requirement.
- High flow oxygen requirement.
- Invasive mechanical ventilation (via endotracheal tube or tracheostomy tube) requirement.
- ECMO requirement.
- Ongoing medical care preventing hospital discharge (COVID-19 related or other medical conditions).
- Limitations of physical activity (self-assessed).
- Isolated for infection control purposes.

8.1.2.2 Ordinal Scale

The ordinal scale is the primary measure of clinical outcome.

The scale used in this study is as follows (from worst to best):

- Death;
- Hospitalized, on invasive mechanical ventilation or ECMO;
- Hospitalized, on non-invasive ventilation or high flow oxygen devices;
- Hospitalized, requiring supplemental oxygen;
- Hospitalized, not requiring supplemental oxygen – requiring ongoing medical care (COVID-19 related or otherwise);
- Hospitalized, not requiring supplemental oxygen – no longer requires ongoing medical care;
 - This would include those kept in hospital for quarantine/infection control, awaiting bed in rehabilitation facility or homecare, etc.
- Not hospitalized, limitation on activities and/or requiring home oxygen;
- Not hospitalized, no limitations on activities

To determine a subject's clinical status using the ordinal scale: On Day 1, report their clinical status at randomization. As there should be <24 hours between randomization and infusion, the ordinal scale at done at randomization suffices as the Day 1 ordinal scale. After Day 1, collect the ordinal scale daily while hospitalized from Day 2 through Day 29 by providing the worst clinical assessment for the previous day (i.e., midnight to midnight; 00:00 – 23:59 (24-hr clock)). For those who are discharged prior to Day 15, collect ordinal scale on follow-up Days 15, 22 and 29 by providing the worst clinical assessment for the previous day (i.e., midnight to midnight; 00:00 – 23:59 (24-hr clock)). For example, on study Day 3 when completing the form, the worse

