8.1.2.2 Ordinal Scale

The ordinal scale is the primary measure of clinical outcome.

The scale used in this study is as follows (from worst to best):

- Death;
- Hospitalized, on invasive mechanical ventilation or ECMO;
- Hospitalized, on non-invasive ventilation or high flow oxygen devices;
- Hospitalized, requiring supplemental oxygen;
- Hospitalized, not requiring supplemental oxygen - requiring ongoing medical care (COVID-19 related or otherwise);
- Hospitalized, not requiring supplemental oxygen - no longer requires ongoing medical care;
 - This would include those kept in hospital for quarantine/infection control, awaiting bed in rehabilitation facility or homecare, etc.
- Not hospitalized, limitation on activities and/or requiring home oxygen;
- Not hospitalized, no limitations on activities

To determine a subject's clinical status using the ordinal scale: On Day 1, report their clinical status at randomization. On Day 2, report the period from randomization to midnight on Day 1. On Day 3 through Day 11, or until discharged, and on Days 15, 22 and 29, provide the worst clinical assessment for the previous day (i.e., midnight to midnight; 00:00 – 23:59 (24-hr clock)). For example, on study Day 3 when completing the form, the worse clinical outcome measure of Day 2 is captured with the worst being death followed by ECMO, mechanical ventilation, etc. The Day 2 measurement is assessed as occurring anytime in that 24-hour period (00:00 to 23:59).

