4.3. Efficacy and Safety Variables

For each study day while the patient is hospitalized, the clinical status will be recorded on an 8-point ordinal scale as follows:

- Day 1 – The clinical assessment at the time of randomization.
- Day 2 + - The most severe assessment occurring from midnight to midnight (00:00 to 23:59) of the prior day (e.g., the value recorded on Day 3 will be the most severe outcome that occurred on Day 2).

where the clinical status scale is defined as follows:

- 8. Death;

7. Hospitalized, on invasive mechanical ventilation or ECMO;
6. Hospitalized, on non-invasive ventilation or high flow oxygen devices;
5. Hospitalized, requiring supplemental oxygen;
4. Hospitalized, not requiring supplemental oxygen- requiring ongoing medical care (COVID-19 related or otherwise);
3. Hospitalized, not requiring supplemental oxygen - no longer requires ongoing medical care;
2. Not hospitalized, limitation on activities;
1. Not hospitalized, no limitations on activities

A modified version of the ordinal scale will be used in sensitivity analyses of the primary and secondary outcomes. The modified scale will be as follows:

8. Death;
7. Hospitalized, on invasive mechanical ventilation or ECMO;
6. Hospitalized, on non-invasive ventilation or high flow oxygen devices;
5. Hospitalized, requiring supplemental oxygen;
4. Hospitalized, not requiring supplemental oxygen- requiring ongoing medical care (COVID-19 related or otherwise);
3. Not hospitalized, limitation on activities;
2. Hospitalized, not requiring supplemental oxygen - no longer requires ongoing medical care; or Not hospitalized, no limitations on activities.

That is, category 1 and 3 of the original scale will be combined into the lowest category.

NEWS has demonstrated an ability to discriminate subjects at risk of poor outcomes. This score is based on 7 clinical parameters (see Section 8.1.2.3 in Appendix B of the study protocol). This should be evaluated at the first assessment of a given study day and prior to administration of study product. The 7 parameters can be obtained from the hospital chart using the last measurement prior to the time of assessment and a numeric score given for each parameter (e.g., a RR of 9 is one point, oxygen saturation of 92 is two points). This is recorded for the day obtained. i.e., on Day N, the Day N score is obtained and recorded as the Day N score.

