8.2.4. Incidence of New Oxygen use

The incidence and duration of new oxygen use will be analyzed by treatment arm. This will only include subjects in category 4 at randomization. New use will be identified by a post-enrollment score of at least 5; the number of subjects reporting new use and the incidence rate (and CI) will be reported.

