8.2.6. Incidence of New Non-Invasive Ventilation/High-Flow Oxygen

The incidence and duration of new Non-Invasive Ventilation/High-Flow Oxygen use will be analyzed by treatment arm. This will only include subjects in category 4 or 5 at randomization. New use will be identified by a post-enrollment score of 6. The number of subjects reporting new use and the incidence rate (and CI) will be reported.

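### In ACTT-2 the Day 2 ordinal form includes hours before randomisation, so a patient stepped down earlier that day can be counted as having new respiratory support

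*Protocol*

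**What the plan says.** **Baseline.** Protocol Appendix B 8.1.2.2: "On Day 1, report their clinical status at randomization". The Day 1 score is a single moment, not a period.

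**Later forms.** The same section tells sites to "collect the ordinal scale daily while hospitalized from Day 2 through Day 29 by providing the worst clinical assessment for the previous day", and defines that day as midnight to midnight. SAP 4.3 gives the same rule for Day 2 onward: "The most severe assessment occurring from midnight to midnight (00:00 to 23:59) of the prior day". Neither makes an exception for the Day 2 form.

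**ACTT-1.** Protocol Appendix A 8.1.2.2 did make one: "On Day 2, report the period from randomization to midnight on Day 1". Appendix B has no such sentence, and the amendment history gives no reason for the difference.

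**Timing on Day 1.** Appendix B 8.1.1 allows baseline work and dosing soon after screening: "the initial study product administration can occur on the same calendar day as the screening procedures". Randomisation can therefore fall well into calendar Day 1.

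**New use.** SAP 8.2.4, for oxygen: "This will only include subjects in category 4 at randomization"; "New use will be identified by a post-enrollment score of at least 5". SAP 8.2.6, for category 4 or 5 at randomisation: "New use will be identified by a post-enrollment score of 6". SAP 8.2.8 applies the same rule with a score of 7 to categories 4, 5 and 6.

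**The concern.** The risk set for each new-use endpoint is fixed at randomisation, but the first later form looks back to midnight before it. Suppose a patient was on a higher level of support that morning and had been stepped down by randomisation. The patient enters the risk set on the lower category and is then flagged by the Day 2 form for support that had already ended.

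These endpoints are listed secondary objectives meant to describe progression after enrolment. Support that ended before randomisation cannot be affected by baricitinib. Counting it raises the reported incidence in both arms and pulls the contrast toward zero. It also adds a day to duration of new use, because SAP 3.3.6 to 3.3.8 count days by score and Table 42 summarises days among those flagged as new users. The new-use rows are then not fully comparable with ACTT-1, although SAP Section 15 gives consistency across the stages as an aim.

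**Working it through.** The plan states no figure on this point, so there is none to reproduce. The check is a trace of the scoring rules followed by an illustration of size.

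**Step 1: trace one patient.** Oxygen from 00:00 to 09:00 on Day 1, none afterwards, randomised at 15:00.

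| Rule | Window of the Day 2 form | Day 1 score | Day 2 form score | New oxygen use under SAP 8.2.4 |
|---|---|---|---|---|
| ACTT-2 | 00:00–23:59 of Day 1 | 4 | 5 | Yes |
| ACTT-1 wording | 15:00–midnight of Day 1 | 4 | 4 | No |

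Nothing changed after randomisation, yet the ACTT-2 rule records new use. Here 15/24 = 62.5% of the window precedes randomisation; for randomisation at 06:00, 12:00 or 18:00 the share is 25%, 50% or 75%.

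**Step 2: who is affected.** Support still in use at randomisation sets the Day 1 score and puts the patient outside that endpoint's risk set. Only a patient stepped down earlier on the same calendar day is misclassified. For ventilation/ECMO that means coming off it and being randomised within one day, so this is probably the rarest case.

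**Step 3: size.** Let p be the true incidence of new use, and q the share of at-risk patients without genuine new use who are wrongly flagged, taken as equal in both arms. Then:

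- observed incidence = p + (1−p)q = 1 − (1−p)(1−q)
- observed risk difference = (1−q) × true difference

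The documents give neither p nor q. With assumed p of 20% and 30%:

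| q (assumed) | Lower arm | Higher arm | Difference |
|---|---|---|---|
| 0 | 20.0% | 30.0% | 10.0 points |
| 2% | 1 − 0.80×0.98 = 21.6% | 1 − 0.70×0.98 = 31.4% | 9.8 points |
| 5% | 1 − 0.80×0.95 = 24.0% | 1 − 0.70×0.95 = 33.5% | 9.5 points |
| 10% | 1 − 0.80×0.90 = 28.0% | 1 − 0.70×0.90 = 37.0% | 9.0 points |

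The difference is the relevant scale: Protocol Appendix B 9.4.3 plans differences in proportions for binary outcomes, and the SAP plans incidence with a confidence interval per arm.

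**Step 4: primary endpoint.** Recovery needs a score of 1, 2 or 3, and patients enter at 4 to 7. A window starting at randomisation still contains the randomisation status, so its worst score is at least 4 under either rule. Changing the window does not create or remove a recovery on that form.

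**The case against.** Four points deserve weight.

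- **The term is undefined.** The SAP does not say what a *post-enrollment score* is. SAP 3.3.2 and 3.3.4 date events by the day assessed, not the day of collection. Applied here, that would place the Day 2 form on Day 1, and it might not count as post-enrolment. But those sections concern time-to-event outcomes. Dating the form to Day 1 also does not cut its window at randomisation, and dropping it would lose genuine escalation later on Day 1. The ambiguity stands; it needs a sentence either way.
- **The Manual of Procedures may limit the Day 2 entry.** Appendix B 8.1.2.2 refers to it for ordinal-scale data, and it was not available to check. The protocol and SAP themselves state the rule without limit.
- **The effect may be small.** The range for q is an assumption. If stepped-down patients are also the ones likely to escalate genuinely later, fewer flags are false and the effective q is lower.
- **The endpoints are descriptive.** The SAP plans no test for them and no multiplicity adjustment.

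A reader might infer that all support given before enrolment is counted as new, that one arm is favoured, or that the primary result is in doubt. The documents support none of these. Support continuing at randomisation is excluded by the risk set, the misclassification arises before treatment and is balanced in expectation, and recovery is hardly touched. Nor should the size be read from a risk ratio, which would move from 0.67 to 0.76 at q = 10%; that is not the planned measure.

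**Conclusion.** The point holds within limits. Followed as written, Appendix B 8.1.2.2 and SAP 4.3 let the Day 2 form record support that ended before randomisation, and the literal reading of SAP 8.2.4, 8.2.6 and 8.2.8 counts it as new use. Only patients stepped down on the calendar day of randomisation are affected. The error inflates incidence in both arms and shrinks the risk difference by the factor (1−q): from 10.0 to between 9.8 and 9.0 points for assumed incidences of 20% and 30% and assumed q of 2% to 10%.

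This rests on Day 1 being the calendar day of randomisation, on the literal reading of the SAP term, on q being equal between arms, and on the Manual of Procedures not already limiting the entry. Severity is low to moderate: the endpoints are secondary and descriptive.

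**What to change.** **Preferred.** Restore the ACTT-1 sentence in Appendix B 8.1.2.2 and SAP 4.3, so that the Day 2 form reports the worst status from randomisation to midnight at the end of Day 1. The cost is one sentence in each document.

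**If forms are already complete.** State in SAP 8.2.4, 8.2.6 and 8.2.8 that a Day 2 form score counts as new use, and toward its duration, only if that support is confirmed to have been in use after randomisation. Sites need to check only at-risk patients whose Day 2 score meets the new-use threshold.

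**Not as the main rule.** Starting new use at the Day 3 form should be a sensitivity analysis only. It loses escalations that begin and end between randomisation and midnight on Day 1, and it also loses some that continue. A patient randomised on nasal cannula, started on high-flow that evening and intubated on Day 2 scores 6 on the Day 2 form and 7 on the Day 3 form. Unless a later form shows a 6, SAP 8.2.6 would miss the new high-flow use. Those losses fall on early deteriorators, whom the endpoint is meant to capture.
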